10.4 Severity

The severity of AEs will be assessed according to the following definitions:

Mild: The Adverse Event is noticeable to the subject but does not interfere with routine activity.

Moderate: The Adverse Event interferes with routine activity but responds to symptomatic therapy or rest.

Severe: The Adverse Event significantly limits the subject's ability to perform routine activities despite symptomatic therapy.

10.5 Reporting

10.5.1 Adverse Events

Only AEs that occur during and after treatment (treatment emergent AEs) will be recorded. At each visit during the trial, AEs that have occurred since the previous visit must be recorded. All subjects will be questioned and evaluated for AEs or complications associated with the procedure. Complications of the injection include, but are not necessarily limited to: pain, swelling and/or inflammation at the injection site. The Investigator will determine the severity and relationship of each event, as defined above.

AEs observed during the course of this study, regardless of severity or relationship to the injection will

be recorded on the appropriate eCRF. Each reported complication/AE will also include the duration, action taken to address the AE, and the resolution status (e.g. ongoing, resolved). These subjects will continue to be evaluated for safety and efficacy at all scheduled follow-up points.

The Sponsor must report the results of an evaluation of an Unanticipated Adverse Device Effect (UADE) to relevant regulatory agencies and all reviewing IRBs and Investigators within timelines required by the regulatory agencies.

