2 DEFINITIONS

Baseline: The assessments performed prior to the study injection after the Screening Visit.

Blinded Evaluator: The Blinded Evaluator will be a physician, research nurse, registered physiotherapist or physician assistant trained by the Principal Investigator (PI) to perform the assessments outlined in the protocol. The Blinded Evaluator will complete the Physical Exam, Physical Evaluation of both knees, Range of Motion (ROM) assessment of both knees, and the Evaluator Global Assessment.

End of Study: End of study is defined as the last subject's last visit.

Enrolled: A Subject who has signed the informed consent form (ICF) is enrolled.

Index Knee: The knee that meets the eligibility criteria for treatment. The Index knee may also be termed the "study knee". In subjects with bilateral knee Osteoarthritis (OA), where both knees meet eligibility criteria, the more symptomatic knee is the Index knee.

Institutional Review Board (IRB) refers to an independent body (e.g. Research Ethics Boards, Independent Ethics Committees) whose responsibility is to ensure the protection of rights, safety and well-being of human subjects involved in a trial. Committees with these responsibilities will be referred to in this document as IRB.

Rescue Medication: Acetaminophen will be distributed as the rescue medication. It is the only medication that should be taken for knee pain during the entire study. Rescue medication will be discontinued at least 48 hours prior to Baseline and all follow-up visits.

Treating Physician: The Treating Physician will most often be the PI. He/she will administer the Cingal[®], Triamcinolone Hexacetonide (TH), or Placebo injection but will not participate in the efficacy evaluation.

Treatment Failure: A Subject who undergoes a procedure or uses a medication (other than the rescue medication) for the treatment of OA in the Index knee at any time after the study injection through the 26-week visit.

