9.2.3 Medical History

A complete Medical History will be obtained at the Screening Visit. The Medical History will include an inquiry of past medical conditions in the following body systems: neurological, psychological, cardiovascular, hematological, respiratory, endocrine/metabolic, musculoskeletal, and immunologic (including allergies). The Medical History will also include an assessment of the subject's history of the following:

- History/duration of knee OA
- History of operative arthroscopies
- History of open surgical procedures of either knee
- History of open surgical procedures of either hip
- History of IA injections including HA and steroid
- History of electromagnetic stimulation therapy
- History of other OA surgeries

Anika Therapeutics, Inc. Cingal 19-01

- History of other OA procedures
- History of other OA abnormalities

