9.2.6 Rescue Medications

Acetaminophen (up to a maximum of 3.0 grams per day per the package insert or as per regional limitations) will be allowed as the rescue medication for the treatment of joint pain for the duration of the study. At least forty-eight hours prior to the Baseline Visit and each follow-up visit the Subject should discontinue use of the Rescue Medication.

At the Screening Visit, the Rescue Medication (i.e. acetaminophen) will be dispensed. The Subject should be instructed to bring the Rescue Medication with them to each follow-up visit for a pill count. Additional Rescue Medication (i.e. acetaminophen) will be dispensed as needed at the follow-up visits.

A medication is considered concomitant if taken after signing the ICF and up to and including the last follow-up visit. Data on medications will include: medication name, dose, unit, route, frequency, start date, stop date, indication and whether the medication was taken for an AE.

At each study visit, the Subject will be asked about any new medications that were started since the last visit. Indications for any new medications during the study period will be recorded as AEs, unless the medications are administered for a pre-existing condition.

Anika Therapeutics, Inc. Cingal 19-01

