10.5.2 Serious Adverse Events/Serious Adverse Device Effects/Serious Adverse Reactions

All SAE/SADE/SAR/ SUSAR must be reported to the Sponsor or designee within 24 hours of the investigative site becoming aware of its occurrence. This requirement is irrespective of whether the SADE/SAE is thought to be possibly related to the CTM/study procedure or not.

SAE/SADE/SAR/ SUSAR Reporting Procedures

Information such as the Investigator name, study name/protocol number, Subject ID number, the name of the SAE/SADE/SAR, the Investigator's assessment as to the relationship to the CTM/study procedure, and the reporting source should be included in the initial report. Any additional supporting documentation (e.g., autopsy report, hospital records, etc.) must be submitted to the Sponsor or designee. This also includes forwarding pertinent follow-up information (e.g., hospital discharge summary) as it becomes available. A completed SAE/SADE/SAR/ SUSAR form needs to be submitted with each follow-up. The Subject must be monitored carefully until the condition disappears, or the etiology is identified.

All SAE/SADE/SAR/ SUSAR will be entered into the EDC system. The EDC system will automatically notify the Medical Monitor and the Sponsor or designee.

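### The protocol gives adverse event recording no single start point, and protocol and SAP define treatment-emergent in two incompatible ways

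*Protocol*

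**What the plan says.** **When recording starts.** Protocol 10.5.1 opens with "Only AEs that occur during and after treatment (treatment emergent AEs) will be recorded". It continues with "At each visit during the trial, AEs that have occurred since the previous visit must be recorded", and later says that "AEs observed during the course of this study, regardless of severity or relationship to the injection will" be entered on the eCRF. Neither of the later sentences is limited to the time after injection.

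Protocol 9.2.6 adds "Indications for any new medications during the study period will be recorded as AEs, unless the medications are administered for a pre-existing condition". The study period is not defined there or in Section 2. The sentence that sets a consent-based start in 9.2.6 concerns drugs: "A medication is considered concomitant if taken after signing the ICF and up to and including the last follow-up visit".

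Protocol 9.2.20 issues the electronic diary at Screening. The diary collects AEs, and site staff review it to decide which AEs belong in the EDC system. Protocol 10.5.2 requires 24-hour reporting of every SAE and adds "This requirement is irrespective of whether the SADE/SAE is thought to be possibly related to the CTM/study procedure or not", with no start point. Section 2 says "A Subject who has signed the informed consent form (ICF) is enrolled". Section 9.2.3 says "A complete Medical History will be obtained at the Screening Visit" and provides for no later update.

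**What treatment-emergent means.** Protocol 10.5.1 uses the term for events during and after treatment. Protocol 11.7 and SAP 4.4 instead define a TEAE as an AE that the investigator places in one of the three related categories. The breakdown by system organ class and preferred term is specified for TEAEs. The count of subjects with any AE, compared between arms by Fisher's exact test, carries no onset condition.

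**The concern.** The 14 ±3 days before Baseline (Protocol 9.3, 9.4) are not passive waiting. Analgesics other than acetaminophen are stopped at Screening, and acetaminophen is dispensed. An event that begins in this interval starts after the medical history is taken and before the recording window in the first sentence of 10.5.1. It has no agreed place in the database.

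Two things are at stake. First, Protocol 6.4 promises the incidence and timing of all AEs, and that record will be incomplete or will vary by site for part of the enrolled period. Second, readers normally take a TEAE table to show what happened after the injection. Under 11.7 and SAP 4.4 it shows only what the investigator thought was related.

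**Working it through.** The plan states no figure on this point, so the check sets the rules side by side, follows sample events through them, and sizes the interval.

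**1. The recording rules applied to a new event between consent and injection**

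| Rule | Recorded as an AE? |
|---|---|
| 10.5.1, first sentence | No |
| 10.5.1, since the previous visit | Yes at Baseline, reaching back to Screening |
| 10.5.1, during the study | Yes |
| 9.2.6 | Yes, if newly medicated, not for a pre-existing condition, and the study period includes the run-in |
| 9.2.20, diary | Noted by the subject; EDC entry depends on site review |
| 10.5.2 (SAEs) | Reportable; no start point given |

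Two sites that each follow a sentence of the protocol can reach opposite answers.

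**2. Sample events**

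- *Run-in event, no new drug, resolved by Baseline.* Excluded by the first sentence of 10.5.1, included by the second, untouched by 9.2.6.
- *Run-in event treated with a new drug.* Excluded by the first sentence of 10.5.1, included by 9.2.6 if the study period starts at consent. Once entered, it counts toward subjects with any AE, because 11.7 and SAP 4.4 give no onset rule to remove it.
- *Post-injection event judged unlikely or not related.* Treatment-emergent under 10.5.1 but not a TEAE under 11.7 or SAP 4.4. It stays in the all-AE counts and the tabulation by relationship, but drops out of the TEAE summaries by system organ class and preferred term.

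**3. Size of the interval**

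Inputs: 231 treated subjects (Protocol 11.1); run-in 14 ±3 days; last visit at 26 weeks ±7 days (182 ±7 days).

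Person-years = 231 × days / 365.25:
- 11 days: 231 × 11 / 365.25 = 7.0
- 14 days: 231 × 14 / 365.25 = 8.9
- 17 days: 231 × 17 / 365.25 = 10.8

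Run-in share of the time from Screening to week 26:
- nominal: 14 / (14 + 182) = 7.1%
- extremes: 11 / (11 + 189) = 5.5% and 17 / (17 + 175) = 8.9%

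These figures cover treated subjects only. Screen failures would add to the person-years, but their number is not given.

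**4. How many events (assumption, for scale only)**

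The documents give no run-in AE rate. Assume a constant rate λ of 0.005 to 0.04 first new events per subject-week. The proportion affected is 1 − exp(−λ × days / 7):
- 14 days: 1.0% to 7.7%, about 2 to 18 of 231
- 11 days at the low rate to 17 days at the high rate: 0.8% to 9.3%, about 2 to 21 of 231

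**5. Effect on the arm comparison**

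Let q be the proportion with a counted run-in event, equal across arms and independent of later AEs, and p the post-injection any-AE proportion. The observed proportion is 1 − (1 − q)(1 − p), so the difference between two arms is (1 − q) times the true difference. With q of 1.0% to 7.7%, and every such event counted, the difference shrinks by that same percentage. It does not change sign.

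**The case against.** The strongest reply is that 10.5.1 is itself the onset cut. If sites obey its first sentence, no pre-injection event enters the database, and 11.7 and SAP 4.4 need no second filter. On that reading the Baseline mark for AE assessment in the Schedule of Events is also consistent: Baseline and Treatment are both Day 0, and Protocol 9.4 names the task as treatment-emergent AEs and lists it after the injection. That part stands, and the Schedule is not counted as a conflict here. The reply fails on the other sentences of 10.5.1 and on 9.2.6 and 9.2.20, which a site may equally follow.

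Three stronger readings are tempting, and the documents do not support them.

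- *Another rule records all events from consent.* It does not. The consent anchor in 9.2.6 applies to medications, and the AE rule beside it reaches only newly medicated conditions that are not pre-existing.
- *Run-in events are lost.* Too absolute. The diary and the concomitant medication record, which notes indication and whether a drug was taken for an AE, keep traces. Nor can one event be both lost and counted in excess, since those outcomes need opposite readings of 10.5.1.
- *Run-in events will look as if the injection caused them.* Protocol 10.3 has the investigator judge causality and classes an event without a reasonable time sequence as not related. A correctly assessed run-in event would stay out of the TEAE tables. Only the any-AE count is exposed.

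It is also fair to say that starting full recording at consent is partly a design choice. The safety analysis covers treated subjects only (Protocol 11.8), so screen failures' events would sit outside it.

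**Conclusion.** The inconsistency is real and should be corrected. The protocol does not settle whether a new event in the 11 to 17 days between Screening and injection is an AE, so such events are not reliably recorded as AEs and handling may differ between sites. The shift from a timing-based to a relatedness-based meaning of treatment-emergent is the more consequential half for reporting. It removes post-injection events judged unlikely or not related from the main coded tables, and it leaves the any-AE count with no onset rule.

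The size is modest: 7.0 to 10.8 person-years of run-in in treated subjects, and perhaps 2 to 21 subjects with a new event under the assumed rates, which the documents neither supply nor exclude. Run-in events precede the injection, and nearly all precede randomization at the Baseline visit, so they should balance across arms. The consequence is for completeness and absolute AE rates, with little expected bias between arms.

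**What to change.** **Protocol 10.5.1, 9.2.6, 9.2.20 and 10.5.2:** reconcile to one stated start point for recording AEs and SAEs. Signature of the consent form fits the enrolment definition in Section 2. Define the study period. Record onset relative to the start of aspiration or injection for every AE; Protocol 10.3 now asks for that timing only for related events.

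**Protocol 11.7 and SAP 4.4:** define a TEAE as an event with onset or worsening at or after the start of aspiration or injection, whatever its judged relationship. Tabulate related events as a subset. Apply the onset rule to the any-AE count, and list earlier events separately, including those in subjects never treated.

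**Cost:** wording in both documents and some extra eCRF entries. These include entries for screen failures, whose number the documents do not give, so the burden goes somewhat beyond the Baseline visit. The change is best made before data collection, because onset that was not captured prospectively may be hard to recover.

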10.5.2 Serious Adverse Events/Serious Adverse Device Effects/Serious Adverse Reactions

All SAE/SADE/SAR/ SUSAR must be reported to the Sponsor or designee within 24 hours of the investigative site becoming aware of its occurrence. This requirement is irrespective of whether the SADE/SAE is thought to be possibly related to the CTM/study procedure or not.

SAE/SADE/SAR/ SUSAR Reporting Procedures

Information such as the Investigator name, study name/protocol number, Subject ID number, the name of the SAE/SADE/SAR, the Investigator's assessment as to the relationship to the CTM/study procedure, and the reporting source should be included in the initial report. Any additional supporting documentation (e.g., autopsy report, hospital records, etc.) must be submitted to the Sponsor or designee. This also includes forwarding pertinent follow-up information (e.g., hospital discharge summary) as it becomes available. A completed SAE/SADE/SAR/ SUSAR form needs to be submitted with each follow-up. The Subject must be monitored carefully until the condition disappears, or the etiology is identified.

All SAE/SADE/SAR/ SUSAR will be entered into the EDC system. The EDC system will automatically notify the Medical Monitor and the Sponsor or designee.

10.5.3 Expedited Reporting

Any unexpected fatal or life-threatening AEs will be reported by the Sponsor or designee to the appropriate Regulatory Authority in accordance with applicable expedited reporting guidelines. Any event considered serious by either the Investigator or Sponsor will be evaluated by the Sponsor for expedited reporting.

10.5.4 Study Discontinuation

Enrollment and treatment may be suspended if a Subject experiences a serious and/or life-threatening AE that is probably or definitely related to the study injection. The study will be suspended if in the opinion of the medical monitor and Sponsor that the safety of subjects is uncertain. The decision to resume enrollment and treatment, permanently discontinue the trial, or otherwise modify the study will be made by the Medical Monitor in consultation with the Sponsor. Additionally, the triggering of the stopping rules will prompt notification to the appropriate regulatory agencies including the Food and Drug Administration (FDA) and the IRBs.

11 STATISTICAL CONSIDERATIONS

The statistical analysis of the study is described in detail in a separate version-controlled prospective Statistical Analysis Plan (SAP). However, the statistical methodology described in this section of the protocol will be the basis for the detailed SAP. It should be noted that this is a pilot study designed to assess the differences between Cingal and TH for change in pain and function scores between Baseline and 26 weeks post treatment. This change in scores will be conducted on multiple assessments and therefore, no formal hypothesis testing will be performed.

11.1 Sample Size

This is a pilot study designed to estimate as the primary assessment, the differences between Cingal and TH with respect to the difference in the change in WOMAC pain score from Baseline to 26 weeks post treatment. For convenience the sample size will be assessed in a 3:3:1 ratio (Cingal: TH: Placebo) with the sample sizes being 99:99:33, for a total sample size of 231 patients treated. It should be noted that if the standard deviation for the difference in change from Baseline in the WOMAC Pain Score between Cingal and TH is approximately 20 points and a difference of 8 points would yield 80% power of detecting that difference. If the difference is 10 points, this sample size yields over 90% power of detecting that difference.

Since the primary analysis in this study is an intent to treat analysis and the missing data for a patient will be imputed using mixed effects models, no dropout rate will be assumed for this study. Thus, the total sample size will be 231 patients treated.

11.2 Primary Efficacy Endpoint

The primary efficacy endpoint is the change from Baseline in knee pain as measured by the WOMAC Pain Score (100 mm VAS).

The time point of main interest is 26 weeks, but in order to study the time course profile, the data will be analyzed at each time point. Data will be analyzed via an Analysis of Variance (ANOVA) with a term for treatment and Baseline pain score as a covariate. The primary analysis will be conducted by constructing 95% confidence intervals using the predefined contrasts for comparing the Cingal® arm to the TH arm, the Cingal arm to the Placebo arm, and the TH arm to the Placebo arm. These confidence intervals will be constructed as:

$$(\overline{X}_{\iota} - \overline{X}_{J}) \pm z_{\alpha/2} s_{D}$$

Where $\overline{X_i}$ and $\overline{X_j}$ are the Least Squares Means for the two treatments being utilized and s_D is the standard deviation of that difference.

11.3 Secondary Efficacy Endpoints

There are many secondary endpoints to be investigated in this study. Again, these endpoints will be evaluated utilizing pairwise confidence intervals. For continuous variables the confidence intervals will be constructed as in section 11.2. For the dichotomous variables, the confidence intervals for the responder rates will be constructed utilizing the normal approximation to the binomial.

11.3.1 OMERACT-OARSI responder

The OMERACT-OARSI response rates for the Cingal® arm, TH arm, and the Placebo arm will be calculated for each time point and all pairwise difference confidence intervals will be constructed utilizing the normal approximation to the binomial distribution [29, 30].

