Cingal® is a sterile, biocompatible, non-pyrogenic, viscoelastic, uniform white/off white opaque solution composed of molecules of HA and Triamcinolone Hexacetonide (TH). Cingal® is intended to treat the pain of OA of the knee in patients who have failed to respond to conservative non-pharmacological therapy and to simple analgesics, e.g., acetaminophen. Cingal® functions as a viscoelastic supplement or a replacement for synovial fluid in human joints with short term pain relief is provided by Triamcinolone Hexacetonide.

Cingal® has been studied in two Phase III trials, Cingal 13-01 and Cingal 16-02, and several follow-on studies, Cingal 13-02 and Cingal 17-02 [14-17]. Cingal® studies generated a safety data base of 642 subjects treated intra-articularly with a Cingal® injection, including 94 subjects retreated with a second injection.

The data supports the safety of Cingal[®]. There were no deaths in any of the trials, and all SAEs were found not related to the study injection. The types of adverse events considered related to the study injection were typical side effects of any intra-articular injection: arthralgia, injection site pain, joint swelling, injection site reaction, joint warmth and decreased ROM. All AEs considered related to the study injection across all studies were transitory and resolved without sequelae.

The integrated analysis of the two Phase III trials showed Cingal reduced WOMAC Pain from Baseline an average of 73% at 26 weeks post-injection.

This clinical trial will determine the contribution of TH to pain relief, both in terms of magnitude and duration, when used within a single injection of Cingal® compared to a single injection of TH in subjects with OA of the knee. A saline placebo is included within the trial to prevent expectation bias by study subjects that could occur in an all-active comparator study.

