11.5 Statistical Methods

Tabulation of summary statistics, graphical presentations, and statistical analyses will be performed using SAS® software 9.1.3 or higher version. Where not otherwise specified, the last pre-treatment observation will be used as Baseline for calculating post-treatment changes from Baseline. The primary presentations and analyses will be based on data pooled across study centers. Relevant summaries for individual centers, or combinations of centers, may be presented for primary data. All confidence intervals will use a significance level of 5%.

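### Normal-approximation intervals for responder differences against the 33-subject placebo arm cover somewhat less than 95%; a Newcombe score interval corrects this, and the SAP table needs interval rows anyway

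*Protocol*

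**What the plan says.** - **Method.** Protocol 11.3 sets the rule for dichotomous secondary endpoints: "the confidence intervals for the responder rates will be constructed utilizing the normal approximation to the binomial". Section 11.3.1 applies it to OMERACT-OARSI response at each time point: "all pairwise difference confidence intervals will be constructed utilizing the normal approximation to the binomial distribution". Neither section names a variance form or a continuity correction.
- **Level.** Protocol 11.5 fixes the error rate for all intervals at 5%, so they are nominal 95% intervals.
- **Arm sizes.** Protocol 11.1 has "with the sample sizes being 99:99:33, for a total sample size of 231 patients treated", so both placebo contrasts are 99 versus 33.
- **Status.** The opening of Protocol section 11 calls the trial a pilot and rules out formal hypothesis testing. Under the protocol, the interval is therefore the only inferential result for this endpoint.
- **SAP.** Section 4.1.3.1 plans Fisher's exact tests for all three pairs at 26 weeks. Its table shell has counts with percentages and p-values, and no difference or interval. Cingal versus TH is labelled primary.
- **Responder rates.** Neither document states an expected responder rate for any arm.

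**The concern.** The Wald interval for a difference in proportions is known to cover less than its nominal level when one arm is small, and more so as the rates approach 0 or 1. Two of the three pairwise comparisons have only 33 subjects in one arm. Because the protocol offers intervals in place of tests, an interval labelled 95% that covers less overstates the certainty of the two placebo contrasts. With equal true rates it also excludes zero more often than 5% of the time. Better intervals need no extra subjects, so the question is how large the shortfall is and whether a change is worthwhile.

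**Working it through.** **The plan's own figure.** The only computed figures are the power statements for WOMAC pain, Cingal versus TH, 99 per arm, SD 20. The standard error is 20 × √(2/99) = 2.843. For 8 points, 8/2.843 − 1.96 = 0.854, giving 80.4% power; for 10 points, 10/2.843 − 1.96 = 1.558, giving 94.0%. Both agree with Protocol 11.1. The responder intervals have no stated figure beyond the nominal 95%.

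**Inputs.** n = 99, 99 and 33 (Protocol 11.1); 95% level (11.5), z = 1.96. True responder rates are *assumed*, because the documents give none.

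**Formulas.** With observed rates p1 and p2 and d = p1 − p2:

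- Wald: d ± z √[p1(1−p1)/n1 + p2(1−p2)/n2].
- Wilson limits (l, u) for one arm: [p + z²/2n ± z √(p(1−p)/n + z²/4n²)] / (1 + z²/n).
- Newcombe: lower = d − √[(p1−l1)² + (u2−p2)²]; upper = d + √[(u1−p1)² + (p2−l2)²].
- Exact coverage: the sum, over all x = 0…n1 and y = 0…n2, of Bin(x; n1, π1) × Bin(y; n2, π2) for outcomes whose interval contains π1 − π2.

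**Results, 99 versus 33** (active rate / placebo rate):

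| Assumed rates | Wald coverage | Newcombe coverage | Mean width, Wald | Mean width, Newcombe |
|---|---|---|---|---|
| 50 / 50 | 94.1% | 95.0% | 0.389 | 0.372 |
| 80 / 50 | 94.1% | 94.9% | 0.371 | 0.355 |
| 70 / 70 | 93.8% | 95.1% | 0.356 | 0.345 |
| 80 / 80 | 93.3% | 95.3% | 0.310 | 0.309 |
| 90 / 80 | 93.3% | 95.6% | 0.291 | 0.292 |
| 90 / 90 | 92.2% | 95.9% | 0.229 | 0.249 |
| 95 / 90 | 91.7% | 95.5% | 0.214 | 0.236 |
| 95 / 95 | 85.8% | 97.3% | 0.162 | 0.205 |

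With equal rates, the chance that the Wald interval wrongly excludes zero is 100% minus coverage: 5.9% at 50%, 6.7% at 80%, 7.8% at 90% and 14.2% at 95%.

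**Over a grid of rates from 30% to 90%.** Wald averages 93.9% (range 92.0-94.3%, mean width 0.353). Newcombe averages 95.0% (94.4-96.1%, mean width 0.343).

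**Results, 99 versus 99.** For the same rate pairs Wald covers 94.5-94.8%; over the 30-90% grid it averages 94.6%. Most of the shortfall therefore comes from the 33-subject arm.

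**Why the 95/95 case is so poor.** At a true placebo rate of 95%, all 33 placebo subjects respond with probability 0.95³³ = 0.184, and the placebo term in the Wald variance is then zero. If 94 of 99 Cingal subjects respond, d = 0.9495 − 1 = −0.0505 and SE = √(0.9495 × 0.0505/99) = 0.0220. The interval is −0.0505 ± 0.0431, or −0.094 to −0.007, which excludes the true difference of zero. At a true rate of 90% the same event has probability 0.90³³ = 0.031.

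**The case against.** **The size depends on rates the documents do not give.** A reader might infer severe undercoverage from the Introduction's statement that pooled earlier trials "showed Cingal reduced WOMAC Pain from Baseline an average of 73% at 26 weeks post-injection". That inference fails: the figure is a mean pain reduction in Cingal subjects only. It is not a responder rate, and it says nothing about placebo, which is the small arm. With Cingal at 90% and placebo at 50%, Wald still covers 94.0%. The design also aims to restrain placebo response, through the training in Protocol 9.2.13.2 and the stated purpose of the saline arm. This stands: 85.8% is an outer bound.

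**The wording need not mean Wald.** A continuity-corrected interval is also a normal approximation, and over rates of 30-90% it covers 95.5-97.0%. This stands as a point of reading. The uncorrected form is the ordinary meaning, however, and the corrected one is wider on average (0.393 against 0.343 for Newcombe). Either way, the method needs a name.

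**Wald intervals are not simply too short.** At mid-range rates they are wider than Newcombe intervals and still cover less. This stands; width explains the shortfall only at high rates.

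**Newcombe is not exact.** Over the 30-90% grid it falls below 95% at about 46% of points, but never below 94.4%. Wald is below 95% at all of them.

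**The consequence is small.** This is a secondary endpoint in an estimation pilot, and the placebo contrasts are not the SAP's main comparison. This stands, and it sets the priority.

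**Conclusion.** The concern holds in moderate form. Read as the uncorrected, unpooled Wald interval, the protocol's method covers less than 95% for both placebo contrasts at every rate pair examined. The shortfall is about 1 percentage point at placebo rates of 50-70%, 1.7 points at 80% and 2.8 points with both rates at 90%. It reaches 9.2 points only with both at 95%. All of these rest on assumed responder rates and arms of 99 and 33 with complete data.

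The documents do not support a claim that the responder results are seriously unreliable, that high placebo response is expected, or that the main Cingal versus TH comparison is compromised. The primary endpoint and sample size are untouched. The point is a low-priority improvement, strengthened by the fact that the SAP currently does not deliver the intervals the protocol promises.

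**What to change.** 1. **Protocol 11.3 and 11.3.1.** Replace the normal-approximation wording with the Newcombe (hybrid Wilson score) 95% interval for all pairwise responder differences.
2. **SAP 4.1.3.1.** There is no interval wording to replace, so add one. Extend the table with a row for each pair giving the difference in responder rates and its 95% Newcombe interval (PROC FREQ, RISKDIFF with CL=NEWCOMBE), and do the same at other visits where the intervals are reported. Reconcile the Fisher p-values with the protocol's statement that no formal testing will be done.
3. **Multiple imputation.** Protocol 11.8 and SAP 4.5 put secondary endpoints on the ITT population with multiple imputation. A Newcombe interval is not an estimate plus or minus a multiple of its standard error, so add one sentence on how it is combined across imputations. One option is to pool each arm's proportion by Rubin's rules, convert the total variance to an effective sample size (the actual n if the pooled rate is 0 or 1), and compute the Wilson limits from that. The choice matters little if missing data stay below the 1% that SAP 4.5 reports from earlier studies.

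**Cost.** No subjects or data collection: one phrase in two protocol sections, new table rows and one sentence in the SAP. Intervals against placebo are slightly narrower at mid-range rates and about equal at 80/80. They are wider at high rates: 0.249/0.229 = 1.09 at 90/90 (about 9%) and 0.205/0.162 = 1.27 at 95/95 (about 27%), which is where the Wald interval falls furthest short.
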